3.2.3.1.1 PRO-CTCAE

The PRO-CTCAE questionnaire will be used to derive patient reporting of CTCAE symptoms. The PRO-CTCAE will only be administered in those countries where a linguistically validated version exists. PRO-CTCAE is an item-bank of symptoms of the CTCAE experienced by patients while undergoing treatment of their cancer that has been converted to subject terms (i.e., CTCAE term “myalgia” converted to “aching muscles”). Six individual items from the PRO-CTCAE item-bank have been selected as being relevant for this study. These include wheezing, palpitations, rash, itchy skin, hives, aching muscles. Furthermore, items grouped based on their associated body system as assigned by the National Cancer Institute [NCI] will be presented.

3.2.3.1.2 PGIS

The Patient’s Global Impression of Severity [PGIS] item is included to assess how a patient perceives his/her overall current severity of cancer symptoms. Patients will choose between 6 response options from “No symptoms” to “Very severe.”

3.2.3.1.3 EQ-5D-5L

The EuroQol 5 dimensions, 5 levels [EQ-5D-5L] index comprises 5 dimensions of health (mobility, self-care, usual activities, pain/discomfort and anxiety/depression). For each dimension, respondents select which statement best describes their health on that day from a possible 5 options of increasing of severity (no problems, slight problems, moderate problems, severe problems, and unable to/extreme problems). A unique EQ- 5D health state is referred to by a 5-digit code allowing for a total of 3125 health states. For example, state 11111 indicates no problems on any of the 5 dimensions. These data will be converted into a weighted health state index by applying scores from EQ-5D value sets elicited from general population samples (the base case will be the United Kingdom valuation set). Where values sets are not available, the EQ-5D-5L to EQ-5D-3L crosswalk will be applied.

In addition to the descriptive system, respondents also assess their health on the day of assessment on a

visual analogue scale [VAS], ranging from 0 (worst imaginable health) to 100 (best imaginable health).

3.2.4 Pharmacokinetic Outcome Variables

3.2.4.1 Calculation or derivation of pharmacokinetic variables

Pharmacokinetic analysis of the plasma concentration data for osimertinib, savolitinib and, if available, their metabolites (e.g. AZ5104 for osimertinib; M2 and M3 for savolitinib) will be performed by QCP, AstraZeneca, or a delegate on behalf of QCP for relevant individuals using standard non-compartment methods. PK analysis will be performed according to AstraZeneca standard SOP, which specifies all the diagnostic parameters to be reported. Actual sampling times will be used in parameter calculations.

Where possible, the following PK parameters will be determined for osimertinib, savolitinib and their metabolites:

- After single dosing: plasma concentration at 1 hour (C1h) and 3 hours (C3h) post-dose
- After multiple dosing at Cycle 3 Day 1: plasma concentration pre-dose (Cpre-dose), and at C1h, C3h, C4h and C6h post-dose. If applicable, AUC_{ss}, C_{ssmax}, C_{ssmin}, t_{ssmax}, CL_{ss/F}, V_{z/F} and t_{1/2} will be calculated for savolitinib, osimertinib and their metabolites.

If possible, the time dependency of the PK on multiple dosing will be assessed by the calculation of the ratios of:

- C_{3h} Cycle 2 Day 1/C_{3h} Cycle 1 Day 1
- C_{pre-dose} Cycle 3 Day 1/C_{pre-dose} Cycle 2 Day 1
- C_{pre-dose} Cycle 6 Day 1/C_{pre-dose} Cycle 2 Day 1
- C_{pre-dose} Cycle 11 Day 1/C_{pre-dose} Cycle 2 Day 1.

For patients receiving savolitinib 300 mg bid, on PK sampling days, samples will be collected following the first dose of the day.

Individual concentration data may be excluded from the analysis for legitimate scientific reasons e.g., mis-dose, vomiting after dose administration, prohibited co-medication. Where a protocol deviation impacts only part of a patient's data, the affected portion of the patient's PK data will be excluded from PK analysis and summary statistics, and the remaining valid data will be utilised. Any excluded data, together with the justification for exclusion, will be clearly documented in the CSR. The concentration and any PK parameter data from this study may be combined with data from other studies in a population PK or PK-PD analysis and, if conducted, will be reported separately from the CSR.

3.2.5 Retrospective IUO Grade MET Testing

Each patient's MET status for FISH10+ and/or IHC90+ will be re-assessed retrospectively utilising Investigational Use Only [IUO] grade testing.

For CSPv1-6, where patients were enrolled using assays validated based on a cut-off of FISH5+ and/or IHC50+, retrospective re-assessment will be done using a cut-off of FISH10+ and/or IHC90+ with the

final validated IUO grade assays. The MET testing used to enroll patients under CSPv1-6 will be used for identifying FISH5+ and/or IHC50+ patients. However, the retrospective IUO grade testing will be used exclusively when identifying FISH10+ and/or IHC90+ patients, for all summaries and analyses for CSPv1-6 patients.

For CSPv7, where Laboratory Developed Tests [LDTs] have been used for patient enrolment using a cut-off of FISH10+ and/or IHC90+, data will be re-assessed using the final IUO grade assay using the cut-off of FISH10+ and/or IHC90+. The testing used to enroll patients under CSPv7 will be used for all summaries and analyses unless otherwise stated. Supplementary analyses will be produced where CSPv7 patients will be identified for FISH10+ and/or IHC90+ MET status by utilising the retrospective IUO grade testing instead.

3.2.6 Biomarker Outcome Variables

3.2.6.1 Calculation or derivation of biomarker variables

Circulating tumour deoxyribonucleic acid [ctDNA] dynamics will be evaluated as a surrogate marker of clinical efficacy.

Patients with detectable Epidermal growth factor receptor [EGFR] mutations at baseline and available data at 6 weeks will be categorised into the following groups of ctDNA status: (1) ctDNA clearance and (2) ctDNA non-clearance. Patients with undetectable EGFR mutations at baseline will be categorised as “uninformative”. Additional guidance is provided in Table 11.

Table 11 Additional guidance for ctDNA status derivation

Detectable EGFR mutation at baseline	Positive pre-dose result for L858R or exon 19 deletion
Evaluable at 6-weeks	1. Detectable EGFR mutation at baseline AND 2. Evaluable result at 6-weeks ^a
ctDNA clearance	1. Evaluable at 6-weeks AND 2. Negative result at 6-weeks
ctDNA non-clearance	1. Evaluable at 6-weeks AND 2. Positive result at 6-weeks

Not evaluable at 6-weeks	Data otherwise not considered evaluable at 6-weeks
Uninformative assessment at baseline	Negative pre-dose result for L858R or exon 19 deletion
Evaluable data at 6-weeks	1. Uninformative assessment AND 2. Positive or negative post-dose result at 6-weeks
Not evaluable data at 6-weeks	1. Uninformative assessment AND 2. Data otherwise not considered at 6-weeks
Missing baseline assessment	No pre-dose result for L858R or exon 19 deletion
Evaluable data at 6-weeks	1. Missing baseline assessment AND 2. Positive or negative result at 6-weeks
Not evaluable at 6-weeks	1. Missing baseline assessment AND 2. Data otherwise not considered evaluable at 6- weeks

a: Evaluable result at 6-weeks = baseline detectable EGFR mutation for L858R AND positive/negative L858R result at 6-weeks, OR, baseline detectable EGFR mutation for exon 19 deletion AND positive/negative exon 19 deletion result at 6-weeks.

Note: Rare cases where a patient is reported to have both L858R and exon 19 deletion mutations at baseline and/or follow-up and the rules above still applicable to declare ctDNA clearance of at least one mutation. Patients with a single mutation at baseline, but the alternative mutation is observed at 6-weeks are considered not-evaluable at 6-weeks, as described in 'a' above.

The absolute change and the percentage change in EGFR mutation ctDNA allele frequencies at Week 6 will be obtained for each patient. The percentage change is calculated as the difference between the allele frequency of EGFR sensitising mutations in ctDNA at Week 6 and the ctDNA at baseline divided by the allele frequency of EGFR sensitising mutations in ctDNA at baseline multiplied by one hundred (i.e., $[Week\ 6\ -\ baseline]/baseline \times 100$). Patients with undetectable EGFR mutations at baseline will be excluded from this analysis. Samples with undetectable EGFR mutations at Week 6 will be interpreted as 0% allele frequency so that the percentage change is 100%.

All other exploratory research variables will be reported separately from the Clinical Study Report and so will be dealt with outside of this SAP.

4 ANALYSIS METHODS

4.1 General principles

The below mentioned general analyses principles will be followed throughout the study:

- Statistical tests will be performed for two-sided hypothesis. All confidence intervals [CI] will use a 95% confidence level unless otherwise stated.
- Descriptive statistics will be used for all variables, as appropriate. Continuous variables will be summarised by the number of observations, mean, standard deviation [SD], median, quartiles (Q1 and Q3), minimum, and maximum. For log transformed data geometric mean [Geomean], geometric SD [gSD], geometric coefficient of variation [gCV%], median, minimum and maximum will be presented. Categorical variables will be summarised by frequency counts and percentages for each category.
- Unless otherwise stated, percentages will be calculated out of the analysis set total.
- Unless otherwise stated, for continuous data, mean, Geomean, median, quartiles as well as LSmeans will be rounded to 1 additional decimal place compared to the original data. The SD, gSD and standard error [SE] will be rounded to 2 additional decimal places compared to the original data. Minimum and maximum will be displayed with the same accuracy as the original data.
- For categorical data, percentages will be rounded to 1 decimal place.
- Ratio and CI of the ratio will be rounded to two decimal points
- P-values will be presented to three decimal points (displayed as “<0.001” for p-values lower than 0.001).
- SAS® version 9.4 (or higher) will be used for all analyses.
- There are two diagnostic populations of analytical interest as follows:
 - All Patients (FISH5+ and/or IHC50+): This population includes patients identified by lower MET biomarker cut offs (≥ 5 MET gene copies or MET:CEP7 ratio ≥ 2 [FISH5+] and/or $\geq 50\%$ of tumour cells staining at strong 3+ intensity [IHC50+])
 - FISH10+ and /or IHC90+: This population includes patients identified by higher MET biomarker cut offs (≥ 10 MET gene copies according to central MET FISH test [FISH10+] and/or $\geq 90\%$ of tumour cells staining at strong 3+ intensity according to central MET IHC test [IHC90+])

The populations are not mutually exclusive, i.e. a patient may be a member of both populations.

- Analyses will be presented by the assigned dosing regimen (i.e., savolitinib starting dose: 300 mg od, 300 mg bid and 600 mg od (in combination with osimertinib), or 300 mg bid + placebo.

4.2 Description of Analysis methods

4.2.1 Demographics, Baseline Characteristics and other patient-specific characteristics

Demographic and baseline characteristics, patient disposition and prior/concomitant/post-treatment medication will be based on the TPAS, SAF and CAS where applicable.

Demographic and Baseline Characteristics

Demographic, baseline characteristics including height, weight, body mass index [BMI] and medical history will be summarised.

The calculation for BMI is:

$$BMI = \frac{weight \ (kg)}{(height \ [m])^2}$$

Descriptive statistics for age at informed consent as a continuous variable and age group (≥ 18 to <50 , ≥ 50 to <65 , ≥ 65 to <75 , ≥ 75 years old), sex, ethnicity and race as categorical variables will be summarised. Age in years will be calculated as the rounded down integer value of [(date of informed consent - date of birth)/365.25)].

The number and percentage of patients with a medical history, including both resolved and ongoing conditions at the time of study entry, will be summarised by the primary system organ class [SOC] and preferred term [PT] in accordance with MedDRA. Patients will only be counted once per MedDRA level and the medical history will be sorted by alphabetically by SOC and PT. Relevant surgical history will be summarised similarly.

The number and percentage of patients recruited by country will be presented. EGFRm subtype status will also be summarised and listed. Disease characteristics will also be summarised and listed.

Patient Disposition

Patient disposition will be summarised for all screened patients. The number and percentage of patients who were screened, received study treatment, had ongoing treatment at data cut-off, discontinued study treatment, and who terminated the study, will be presented.

Patients discontinuing the study and patients ongoing at data cut-off will be listed.

The number of patients included/excluded from each of the analysis sets will be provided. Patients excluded and reason for exclusion from the Target Population Analysis Set, Contribution of Components Analysis Set, Safety Analysis Set, and PK Analysis Set will be listed for all patients who signed the main study ICF.

Prior/Concomitant/Post-treatment Medication

The number and percentage of patients with any concomitant medications summarised by ATC category name (ATC level 4), and generic term (product name) will be provided for the Safety analysis set. Subsequent anti-cancer treatment (including both Post-Treatment Cancer Therapies and Post Treatment Radiotherapies) will be summarised separately in similar tables. The number of regimens of previous

anti-cancer therapies at baseline will be summarised. A table of time (number of days) from the end of previous anti-cancer therapy to the start of study treatment will also be provided.

4.2.2 Efficacy analyses

4.2.2.1 Primary Endpoint - Objective Response Rate

4.2.2.1.1 Target Population Analysis Set

The primary endpoint of ORR as assessed by the investigator per RECIST 1.1 in patients treated with savolitinib 300 mg bid + osimertinib in FISH10+ and/or IHC90+ who have progressed following treatment with 1L osimertinib will be summarised using the TPAS.

The ORR and its associated 2-sided 95% CIs (Clopper-Pearson) will be provided and compared with the historical reference platinum-pemetrexed chemotherapy ORR of approximately 30%. Summaries will be produced that present the number and percentage of patients with a tumour response (CR/PR).

BoR will also be presented and summarised by n (%) for each category (CR, PR, SD, PD and NE).

4.2.2.1.1.1 Subgroup analyses

Subgroups analyses of ORR as assessed by the investigator per RECIST 1.1 will be conducted on TPAS within the following subgroups (Appendix “A”):

- Race [Asian, Non-Asian]
- Sex [Male, Female]
- Age at baseline [<65 years, \geq 65 years]
- T790M status in baseline plasma [T790M+, T790M-]
- C797S mutation in baseline plasma [C797S+, C797S-]
- FISH+ allocation status [Amplified, Polysomy]. Patients can be considered FISH+ by either amplification or polysomy, where amplification is considered a ratio of ‘Mean MET/CEP7 RATIO’ or ‘CEP7/MET RATIO’ \geq 2 and polysomy where ratio $<$ 2. The non-FISH+ patients will be excluded. Ratio information will be provided by external vendors
- IHC+ allocation status [IHC90+, IHC90 negative (FISH10+), IHC50+, IHC50 negative (FISH5+), IHC missing/unknown (FISH+ to enter study)]
- FISH+ allocation status [FISH10+, FISH10 negative (IHC90+), FISH5+, FISH5 negative (IHC50+), FISH missing/unknown (IHC+ to enter study)]
- Overall disease classification [Metastatic, Locally advanced, Missing]
- EGFR mutation status [Exon 19 deletion, L858R]
- Known or treated brain metastases at study entry [Yes (present at baseline or not present at

baseline but with known or treated history of brain metastases), No (not present at baseline and not known or treated history of brain metastases)]. This classification will be identified by an AstraZeneca medically qualified expert during the medical review process

- Eastern Cooperative Oncology Group [ECOG] at baseline [0, 1, ...]
- Histological Type [Adenocarcinoma, Other].

Forest plots of ORR with 95% Clopper-Pearson CI for each subgroup will also be produced.

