4.2.2.4 Secondary Endpoint – Progression Free Survival

4.2.2.4.1 Target Population Analysis Set

PFS will be summarised using the Kaplan-Meier methodology and will be based on TPAS. Median time to progression, and quartiles will be summarised, including 95% CI. The percentage of patients being progression-free at 3, 6, 9, 12, 18, 24, 30 and 36 months, along with the 95% CI, and the median and range of duration of follow-up in censored patients, will also be presented. Kaplan Meier curves will also be plotted.

Treatment status at time of progression will be presented, showing patients who were on savolitinib and/or osimertinib at time of progression and patients who discontinued treatment prior to progression. Treatment status after progression will also be summarised, showing the patients who continued to receive savolitinib and/or osimertinib after progression.

4.2.2.4.1.1 Subgroup analyses

Subgroups analyses of PFS will be conducted on the same subgroups as for ORR and based on TPAS. Refer to section 4.2.2.1.1 for details on the specific subgroups and Appendix “A”.

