8 APPENDICES

Appendix A Subgroup Analysis list

	ORR and PFS	
	TPAS	SAF*
Race		
Asian	X	X
Non-Asian		
Sex		
Male	X	X
Female		

Age group	X	X
<65 years		
>=65 years		
Line of treatment		
2nd line		X
>=3rd line		
Missing		
Prior platinum-based chemotherapy		
Yes		X
No		
Missing		
Prior platinum-based chemotherapy and line of treatment		
Yes and 2nd line		
Yes and >=3rd line		X
No and 2nd line		
No and >=3rd line		
Missing		
Immediately prior line of therapy		
Osimertinib		
Platinum-based chemotherapy		X
Other		
Missing		

Response to immediately prior line of therapy		
Yes and osimertinib		
Yes and platinum-based chemotherapy		
Yes and other		X
No and osimertinib		
No and platinum-based chemotherapy		
No and other		
Missing		
Immediately prior line osimertinib		
Osimertinib		
Not osimertinib		X
Missing		
Response to immediately prior line of therapy, osimertinib		
Yes and osimertinib		
Yes and not osimertinib		
No and osimertinib		X
No and not osimertinib		
Missing		
Number of previous EGFR TKI therapies		
1		
2		X
...		
Missing		
T790M status in baseline plasma	X	X
T790M+		
T790M-		

C797S mutation in baseline plasma		
C797S+	X	X
C797S-		
FISH+ allocation status		
Amplified (i.e., MET/CEP7 RATIO ≥ 2)	X	X
Polysomy (i.e., MET/CEP7 RATIO < 2)		
Missing		
IHC+ allocation status		
IHC90+		
IHC90 negative (FISH10+)	X	X
IHC50+		
IHC50 negative (FISH5+)		
IHC missing/unknown (FISH positive to enter study)		
FISH+ allocation status		
FISH 10+		
FISH 10 negative (IHC90+)	X	X
FISH 5+		
FISH 5 negative (IHC50+)		
FISH missing/unknown (IHC+ to enter study)		
Overall disease classification		
Metastatic	X	X
Locally advanced		
Missing		
EGFR mutation status [d]		
Exon 19 deletion	X	
L858R		

Known or treated brain metastases at study entry		X	
Yes (present at baseline or not present at baseline but with known or treated history)		X	
No (not present at baseline and not known or treated history of brain metastases)			
ECOG at baseline	0	X	
	1		
...			
Histological type		X	
Adenocacinoma			
Other			

* SAF : savolitinib 300 mg od + osimertinib (FISH10+ and/or IHC90+)

	OS		
	TPAS	SAF*	CAS
IHC+ allocation status			
IHC90+			
IHC90 negative (FISH10+)			
IHC50+	X	X	X
IHC50 negative (FISH5+)			
IHC missing/unknown (FISH positive to enter study)			
FISH+ allocation status			
FISH 10+			
FISH 10 negative (IHC90+)	X	X	X
FISH 5+			
FISH5 negative (IHC50+)			
FISH missing/unknown (IHC+ to enter study)			

* SAF : savolitinib 300 mg od + osimertinib (FISH10+ and/or IHC90+)

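### SAP subgroup text applies one cut-off of 2 to MET/CEP7 or its reciprocal CEP7/MET, in conflict with Appendix A, so some patients could be misclassified in the descriptive amplified/polysomy subgroup

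*SAP*

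**What the plan says.** SAP 4.2.2.1.1.1 lists an amplified/polysomy split among the ORR subgroups for the TPAS. It states "Patients can be considered FISH+ by either amplification or polysomy, where amplification is considered a ratio of" mean MET/CEP7, or of "CEP7/MET RATIO", at or above 2, "and polysomy where ratio" is below 2. It adds: "The non-FISH+ patients will be excluded. Ratio information will be provided by external vendors". The same rule appears in the ORR subgroup list for 300 mg od SAF patients (under 4.2.2.2.2, cited elsewhere in the SAP as 4.2.2.2.2.1) and in 4.2.2.14.1.2, which covers ORR in the TPAS with IUO-grade MET status.

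PFS takes over these groups. SAP 4.2.2.4.1.1 says "Subgroups analyses of PFS will be conducted on the same subgroups as for ORR and based on TPAS", and 4.2.2.4.2.1 does the same for 300 mg od SAF patients.

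Appendix A, to which all these sections refer, gives one direction only: "Amplified (i.e., MET/CEP7 RATIO" at or above 2, and "Polysomy (i.e., MET/CEP7 RATIO" below 2. The FISH5+ definition in SAP 4.1 runs the same way: at least 5 "MET gene copies or MET:CEP7 ratio" of at least 2. FISH10+ is defined by copy number alone.

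**The concern.** MET/CEP7 and CEP7/MET are reciprocals. A high MET/CEP7 means MET is gained relative to chromosome 7; a high CEP7/MET means the opposite. A single threshold of 2 cannot mark amplification on both scales. Because the polysomy limb does not name its ratio, the body text does not by itself define two exclusive groups: every tumour has at least one of the two ratios below 2.

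The text leaves the ratio to outside laboratories, and more than one assay source is in play. SAP 3.2.5 describes retrospective IUO assays for FISH10+ and/or IHC90+ status in patients enrolled under CSP versions 1 to 6, and laboratory-developed tests for enrolment under version 7. SAP 2.1 pools patients from versions 5, 6 and 7 in the 300 mg bid target population. A programmer working from the body text cannot tell how to treat a value that arrives under the inverse label.

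At stake is whether the ORR and PFS results by amplification and polysomy describe the groups they name.

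**Working it through.** The plan states no figure for this subgroup, so there is none to reproduce. The check classifies tumours under each possible reading.

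**Inputs.** Cut-off of 2 and both ratio names: SAP 4.2.2.1.1.1. Single-direction rule: Appendix A. FISH5+ (at least 5 MET copies, or MET/CEP7 at least 2) and FISH10+ (at least 10 MET copies): SAP 4.1. The copy numbers below are illustrative; the documents give no distribution.

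**Step 1, the algebra.** CEP7/MET = 1 ÷ (MET/CEP7).
- CEP7/MET ≥ 2 is the same as MET/CEP7 ≤ 0.5.
- MET/CEP7 ≥ 2 is the same as CEP7/MET ≤ 0.5.
- Both ratios cannot be at least 2, because their product is 1 and would have to be at least 4.

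**Step 2, three readings.** (A) Appendix A: amplified if MET/CEP7 ≥ 2. (B) The literal rule: amplified if either ratio ≥ 2, otherwise polysomy. (C) Inverse only: amplified if CEP7/MET ≥ 2, as would follow if a source supplied only that value and the cut-off were applied to it unchanged.

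| MET | CEP7 | MET/CEP7 | CEP7/MET | (A) | (B) | (C) |
|---|---|---|---|---|---|---|
| 12 | 2 | 6.0 | 0.17 | Amplified | Amplified | Polysomy |
| 12 | 3 | 4.0 | 0.25 | Amplified | Amplified | Polysomy |
| 10 | 5 | 2.0 | 0.50 | Amplified | Amplified | Polysomy |
| 6 | 5 | 1.2 | 0.83 | Polysomy | Polysomy | Polysomy |
| 12 | 10 | 1.2 | 0.83 | Polysomy | Polysomy | Polysomy |
| 5 | 10 | 0.5 | 2.0 | Polysomy | Amplified | Amplified |
| 10 | 20 | 0.5 | 2.0 | Polysomy | Amplified | Amplified |

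All seven are FISH5+. A tumour with 3 MET and 6 CEP7 copies also has CEP7/MET = 2.0, but it is not FISH+ and is excluded.

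**Step 3, who moves under (B).** No amplified tumour moves, because MET/CEP7 ≥ 2 already satisfies the first limb. Only FISH+ tumours with MET/CEP7 ≤ 0.5 change, from polysomy to amplified. Such a tumour can be FISH+ only by copy number. So CEP7 must be at least 2 × 5 = 10 if FISH+ means FISH5+, or at least 2 × 10 = 20 if it means FISH10+.

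**Step 4, who moves under (C).** Every tumour with MET/CEP7 ≥ 2 moves to polysomy, which is 100% of amplified tumours from that source. Tumours with MET/CEP7 above 0.5 and below 2 stay polysomy. Only those at 0.5 or less move to amplified.

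**The case against.** The strongest reply is that the SAP already contains the right rule. Each subgroup section points to Appendix A, which uses MET/CEP7 only, and the SAP's amendment history records that the subgroup section was aligned with that appendix. The two ratio names appear in capitals and quotation marks next to a statement about vendors, so they may be field labels for one underlying quantity, and the unnamed ratio in the polysomy limb fits that. Nothing in the documents says that any vendor supplies only the inverse. The split is one of many descriptive subgroups, and no test is specified for it.

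Most of this stands. It makes the fault an inconsistency between body text and appendix, not a single wrong rule, and it limits the impact. It does not remove the fault: the SAP never says that the second name is only a label, nor which text governs, and the conflicting wording stands in three places.

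A reader might infer that the rule reverses the subgroup. The documents do not support that. Under the literal reading amplified tumours stay amplified; under inverse-only data most patients would be expected to fall into polysomy, because ordinary polysomy does not move. Nor do they support the inference that the error would bear on the FISH10+ cut-off, which is copy number only and was set before this analysis.

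**Conclusion.** The point holds as an internal inconsistency that can misclassify patients. The body text conflicts with Appendix A and with the FISH5+ definition, and it does not say which ratio sets the polysomy limit.

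The size depends on what the vendors supply. With both ratios available and the rule read literally, only FISH+ tumours with MET/CEP7 of 0.5 or less are misclassified. That these are few is a judgement from the CEP7 counts required (at least 10, or 20 for FISH10+), since no distribution is given. With only a true CEP7/MET value from some source, and Appendix A not followed, all amplified tumours from that source are misclassified. If the second name is a mislabelled field holding MET/CEP7, nobody is. The documents do not settle which case applies, so the number of patients affected cannot be computed.

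The reach is ORR and PFS in the TPAS and in 300 mg od SAF patients, plus ORR by IUO status in the TPAS; the IUO section on PFS (4.2.2.14.2) lists no subgroups. Neither primary ORR analysis, nor membership of the TPAS, uses this split. It should be corrected, but it does not threaten the trial's main conclusions.

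**What to change.** In SAP 4.2.2.1.1.1, 4.2.2.2.2.1 and 4.2.2.14.1.2, define Amplified as MET/CEP7 of at least 2 and Polysomy as MET/CEP7 below 2, matching Appendix A, and remove the inverse ratio from the rule. Add one sentence: any vendor value recorded as CEP7/MET is inverted before classification or, if the field is only mislabelled, is confirmed as MET/CEP7 against the mean MET and CEP7 copy numbers.

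The cost is a wording change in three bullets, one line of derivation code, and a query to each vendor about what the field contains. If the subgroup has already been programmed, check which ratio was used.
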